7.8.2 Prohibited concomitant treatments (medications and therapies)

Prior medication exclusions and washout periods are listed in [Section 6.2](#). In addition, use of the following concomitant medications is prohibited during the study, except where indicated:

- Corticosteroids (administered oral, iv/ia) are permitted only as described in [Section 7.8.1](#). Intramuscular corticosteroids and SIJ ia corticosteroid injections are not permitted.
- Hyaluronic acid may be used as ia injection in the knee only.
- Specific SAARDs (cyclosporine, cyclophosphamide, mycophenolic acid, apremilast).
- Biologicals (TNF antagonists: IFX, ADA, ETN, GOL; abatacept [ABA]; CZP; Rituximab or other anti-CD20 antibodies; tocilizumab; ustekinumab; tofacitinib; also any other biological response modifiers which are not licensed for the treatment of AS or axSpA).
- All iv bisphosphonates (zoledronic acid, ibandronate, pamidronate) are excluded.

Subjects must not participate in any other clinical study for any indication or receive any unauthorized medication during the Study Period.

If the subject requires any of the medications specified in this section, the subject must be withdrawn from the study prior to the initiation of these medications.

The administration of live vaccines is not recommended for subjects treated with TNF antagonists. Live vaccines should not be administered 8 weeks prior to Baseline. If immunization with a live organism-based vaccine is considered during the study, the clinician is urged to carefully weigh the risks vs benefits of immunization. If the subject is going to proceed with live organism-based immunization, the subject must be withdrawn from the study prior to administration of the vaccine. Such vaccines must be recorded in the eCRF.

7.8.3 Rescue medication

[figure not shown]
Escape treatment is as described in [Section 5.1.3](#).

7.9 Blinding

Due to differences in presentation and viscosity between active and placebo, special precautions will be taken in order to ensure blinding of the study during Part B. The subject will receive the IMP throughout the study duration for each single administration in a sealed box with a PFS containing either CZP 200mg or placebo. Packaging and labeling will be done in a way to ensure that the provided box including the PFS will not provide any information about the assigned treatment of the study (CZP 200mg or placebo). Administration of the IMP will be done according to the schedule of study assessments ([Table 5.1](#)) either onsite by appropriately trained unblinded study personnel or at home by the unblinded home nurse.

The injection schedule can be seen in [Figure 7.1](#).

Figure 7.1: Injection Schedule

CZP=certolizumab pegol; PBO=placebo; Q2W=every 2 weeks; Q4W=every 4 weeks; W=Week

7.9.1 Procedures for maintaining and breaking the treatment blind

7.9.1.1 Maintenance of study treatment blind

All subject treatment details will be allocated and maintained by the IXRS.

Part B of the study will be double blind and placebo controlled for 48 weeks. No study team member involved in the clinical conduct will have access to the randomization schedule until after database lock and unblinding.

7.9.1.2 Breaking the treatment blind in an emergency situation

All Sponsor, Investigator site, and Contract Research Organization (CRO) staff involved with the study will be blinded to the treatment code until the database lock (ie, after completion of the Double-Blind Period) with the following exceptions:

- Sponsor clinical study supplies coordinator, packager, and qualified person
- Pharmacy monitors who monitor unblinded pharmacy documentation
- Sponsor pharmacovigilance staff reporting serious adverse events (SAEs) to regulatory authorities
- Emergency service provider staff at the 24/7 SAE reporting hotline
- Laboratory staff analyzing blood samples for CZP plasma concentrations and ADA_b
- Site study medication administrator

The appropriate persons (Investigators, Single Safety Case Management (SSCM) - Safety Officer, Medical Monitor) will be provided with an individual password to access the IXRS menu that will enable them to unblind a subject's double-blind treatment allocation. This password must be kept confidential and not shared with any other persons. The IXRS will be able to identify the individual who has unblinded a subject's treatment allocation. The IXRS will be accessible at all times. If possible, Investigators are advised to contact the company or its representatives prior to unblinding the treatment allocation of subjects.

Under normal circumstances, the blinded treatment must not be revealed. In the case of a medical emergency, UCB or its representatives preferably should be contacted prior to any unblinding. The blind should be broken only if doing so will change the decision making as to the subject's treatment or clinical intervention. Any unblinding performed by the Investigator of the IMP must be documented and explained by the Investigator. If the blind is broken, the date, the reason for the breaking the blind, and person doing so must be recorded. UCB or its representatives must be notified immediately if the blind is broken.

In the event of an emergency, it will be possible to determine to which treatment arm and dose the subject has been allocated by contacting the IXRS. All sites will be provided with details of how to contact the system for code breaking at the start of the study. The Medical Monitor or equivalent should be consulted prior to unblinding, whenever possible.

For the product and study information and emergency unblinding purposes, the Sponsor will provide each Investigator with an appropriate quantity of clinical study subject cards. Each subject will be instructed to keep the card with him/her at all times. These subject cards will be written in the language of the subject. The Investigator will fill in each card with the details of

his/her contact information (eg, Investigator stamp) and subject identifier. The card will be distributed to the subject at the time of informed consent.

The Clinical Project Manager (CPM) or designee will be informed immediately via the IXRS when a code is broken, but will remain blinded to specific treatment information. Any unblinding of the IMP performed by the Investigator must be recorded in the source documents and on the Study Termination eCRF page.

7.10 Randomization and numbering of subjects

An IXRS will be used for assigning eligible subjects to a treatment regimen based on a predetermined production randomization and/or packaging schedule provided by the CRO. The IXRS will generate individual assignments for subject kits of IMP, as appropriate, according to the visit schedule.

To enroll a subject (Screening), the Investigator or designee will contact the IXRS and provide brief details about the subject to be enrolled. Each subject will receive a 5-digit number assigned at screening that serves as the subject identifier throughout the study. The subject number will be required in all communication between the Investigator or designee and the IXRS regarding a particular subject. Subject numbers and kit numbers will be tracked via the IXRS.

The stratification for mNY classification will have the following 2 levels:

- mNY-positive
- mNY-negative

For enrollment in Part A, the IXRS will be designed to ensure that at least 45% and no more than 55% of the subjects belong to each of the 2 clinical subgroups above. Throughout the study, IXRS will be used for the calculation of ASDAS.

To randomize a subject (Week 48), the Investigator or designee will contact the IXRS and provide brief details about the subject to be randomized. The IXRS will automatically inform the Investigator or designee of the subject's randomization number. The IXRS will allocate kit numbers to the subject based on the subject number during the course of the study.

Randomization will be stratified on:

- Geographic region (North America, Western Europe, Eastern Europe, and Asia)
- mNY classification

In order to eventually end up with 210 subjects in sustained clinical remission qualifying for Part B, the enrollment will be adjusted accordingly. For such, the ASDAS will be monitored during Part A at various timepoints to predict the expected percentage of enrolled subjects responding well to the treatment and likely to achieve sustained remission at the end of Part A.

Subjects will be allocated to treatment during Part B in a 1:1:1 ratio (CZP 200mg Q2W: CZP 200mg Q4W: placebo).

8 STUDY PROCEDURES BY VISIT

Section 5.2 (Schedule of assessments) provides a general overview of study assessments. A detailed listing of procedures to be undertaken at each visit is described below.

During the study, the Investigator will assess each subject over the entire study period of up to 109 weeks including a SFU Period of 10 weeks after the last dose. Visit windows of ± 3 days on either side of the scheduled dosing are permitted; however, the Investigator should try to keep the subjects on the original dosing schedule. The window of ± 3 days is relative to Baseline and applicable for all subsequent visits. Changes to the dosing schedule outside of the 3-day window must be discussed with the Medical Monitor and may result in subject withdrawal. For the conduct of MRI, the acceptable time window is ± 2 weeks.

8.1 Screening Visit (up to 5 weeks)

Prior to any study activities, subjects will be asked to read and sign an informed consent form for participation in the study AS0005 and - optional - for obtaining pharmacogenomic samples. All informed consent forms have been approved by an IEC/IRB and the Sponsor and comply with regulatory requirements. Subjects will be given adequate time to consider any information concerning the study given to them by the Investigator or designee. As part of the informed consent procedure, subjects will be given the opportunity to ask the Investigator any questions regarding potential risks and benefits of participation in the study.

Assessments at the Screening Visit include:

- Review inclusion/exclusion criteria
- Confirm informed consent
- Demographic data (includes date of birth, gender, race/ethnicity)
- Washout of prohibited medications
- Significant past medical and procedure history and concomitant disease (includes allergy and any current symptoms); axSpA history; history of extra-articular manifestations (including number of extraarticular episodes during the previous 12 months for psoriasis and IBD and 24 months for uveitis before Screening)
- Vital signs (pulse rate, systolic and diastolic blood pressures, temperature and respiratory rates)
- Hematology, biochemistry, and urine for clinical laboratory values (includes a serum pregnancy test for women of childbearing potential, HLA-B27 and testing to rule out hepatitis B surface antigen, antibodies to hepatitis C, antibodies to HIV, and CRP)
- Physical examination (including weight, evaluation of signs and symptoms of active TB and risk factors for exposure to TB)
 - Screening chest x-ray must have occurred within 3 months prior to Screening
 - TB test: IGRA test (QuantiFERON TB GOLD test [or another WHO-validated IGRA test such as Elispot test only when QuantiFERON test indicated but not available]).
 - TB evaluation questionnaire

- Sacroiliac joint x-ray (centrally read). An SIJ x-ray performed \leq 12 months prior to the Baseline Visit maybe used as the Baseline assessment provided that the film can be submitted and meets the requirements for central reading.
- MRI (centrally read)
- BASMI and Spinal mobility assessments
- BASDAI
- PtGADA
- Prior medications
- Fecal sample kit provided to the subject
- Contact the IXRS to indicate the subject has been screened

The period between the Screening and Baseline Visits must not exceed 5 weeks. The Screening chest x-ray should be read by a radiologist or pulmonologist and must exclude evidence of TB. The qualifying CRP levels from the Screening Visit will be used for the Inclusion Criteria review at Baseline. One retesting of CRP is permitted during the Screening Period in order to meet the Inclusion Criteria.

Subjects who initiate treatment for LTB infection during the Screening Period must repeat initial screening laboratory parameters, all examinations, and questionnaires (after receiving at least 4 weeks of treatment for LTB infection) prior to randomization in the study, and must plan to continue the full course of therapy. It is recommended that the QuantiFERON TB GOLD test be the first test performed at Screening to reduce the number of screening procedures conducted for any QuantiFERON positive subjects that may need to be treated for TB prophylaxis or potentially withdrawn from the study. The Investigator must assess that the subject's likelihood of completing the therapy is high and duly record their opinion in the subject's record prior to randomizing the subject.

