6.2 Exclusion criteria

Subjects are not permitted to enroll in the study if any of the following criteria is met:

1. Subject has previously participated in this study or subject has previously been assigned to treatment in a study of the medication under investigation in this study.
2. Subject has participated in another study of an investigational medicinal product (IMP) (or a medical device) within the previous 3 months (or five half-lives whichever is greater) or is currently participating in another study of an IMP (or a medical device).
3. Subject has history of chronic alcohol abuse or drug abuse within the last year.
4. Subject has any medical or psychiatric condition that, in the opinion of the Investigator, could jeopardize or would compromise the subject's ability to participate in this study.
5. Subject has a known hypersensitivity to any components of the IMP or comparative drugs as stated in this protocol.

AxSpA disease-related exclusions

6. Subjects must not have fibromyalgia or total spinal ankylosis ("bamboo spine"), or any other inflammatory arthritis, eg, RA, systemic lupus erythematosus, sarcoidosis.
7. Subjects must not have a secondary, noninflammatory condition (eg, osteoarthritis) that in the Investigator's opinion is symptomatic enough to interfere with evaluation of the effect of study medication on the subject's primary diagnosis of axSpA.

Prior medications exclusions

8. Subjects must not have used the following medications in the manner as detailed by the Exclusion Criteria in the following table.

Table 6.1: Concomitant Medications (Prior to Baseline and Study Visits)

Drug class	Dose	Exclusion criteria	Study Visits
Analgesics (including, but not limited to acetaminophen, paracetamol, opiates, or combinations thereof)	Up to maximum approved dose	Any change in stable dose regimen is excluded in the 14 days prior to the Baseline Visit.	Any ad hoc (prn) use of analgesics is not permitted within 24 hours prior to any postscreening visit. Stable dose of analgesics (including narcotics) are permitted throughout the study.

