 - History of active TB infection involving any organ system or findings in other organ systems consistent with TB infection
 - Any evidence by radiography or other imaging modalities consistent with previously active TB infection that is not reported in the subject's medical history.
 - b. High risk of acquiring TB infection is defined as:
 - Known exposure to another person with active TB infection within the 3 months prior to Screening
 - Time spent in a healthcare delivery setting or institution where individuals infected with TB are housed and where the risk of transmission of infection is high.

c. Latent TB infection (unless appropriate prophylaxis is initiated prior to study treatment and continued to completion of prophylaxis). Please refer to [Section 12.7.3](#) for further details and instructions.

17. Subjects with current acute or chronic viral hepatitis B or C or with human immunodeficiency virus (HIV) infection.

18. Subjects with current or a history of active infection with histoplasma, coccidioides, paracoccidioides, pneumocystis, nontuberculous mycobacteria, blastomyces, or aspergillus

19. Subjects must not have had a history of an infected joint prosthesis any time.

20. Subjects receiving any live (includes attenuated) vaccination within the 8 weeks prior to Baseline (eg, inactivated influenza and pneumococcal vaccines are allowed but nasal influenza vaccination is not allowed).

21. Subjects who, in the Investigator's opinion, have a high risk of infection (eg, subjects with leg ulcers, indwelling urinary catheter, persistent or recurrent chest infections, and subjects who are permanently bedridden or wheelchair bound).

22. Subjects with a history of a lymphoproliferative disorder including lymphoma or current signs and symptoms suggestive of lymphoproliferative disease.

23. Current malignancy or a history of malignancy, although subjects with less than 3 completely excised basal cell carcinomas or with cervical carcinoma *in situ* successfully surgically treated more than 5 years prior to Screening may be included.

24. Subjects with Class III or IV congestive heart failure as per the New York Heart Association (NYHA) 1964 criteria.

25. Subjects with a history of or suspected demyelinating disease of the central nervous system (eg, multiple sclerosis or optic neuritis).

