8.2 Baseline Visit (Week 0)

Subjects qualifying for this study will have the following procedures performed/recorded prior to study medication administration:

- Review of inclusion/exclusion criteria (The qualifying CRP levels from the Screening Period will be used for the inclusion criteria review at Baseline.)
- Vital signs (pulse rate, systolic and diastolic blood pressures, temperature and respiration rates)
- Blood samples will be collected for hematology, biochemistry analyses, serum calprotectin, and CRP
- Urine will be collected for urinalysis and for a urine pregnancy test for women of childbearing potential
- Physical examination (including extra-articular assessments, height, and weight)
- TB questionnaire

- BASMI and spinal mobility
- BASDAI
- BASFI
- SF-36
- ASQoL
- EQ-5D
- MASES
- Total spinal pain NRS and nocturnal spinal pain NRS
- Swollen and tender joint counts
- PtGADA
- PhGADA
- WPS
- Resources utilization
- IBD-Q
- Plasma sample for CZP concentration, ADAb
- Plasma sample for biomarkers, if applicable
- Genetics/epigenetics, proteomics if applicable
- Stool sample provided by the subject for fecal calprotectin evaluation
- Prior medications
- AEs
- Contact IXRS to randomize subject and to obtain kit number
- Study drug administration (after all other visit assessments are completed and laboratory samples are drawn)

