- Genomics and proteomics (at Weeks 12, 24, 72, and at Week 96/WD only), if applicable.
- Stool sample will be collected for fecal calprotectin at Week 48 and at Week 96/WD only.
- Blood sample will be collected for serum calprotectin at Week 12, Week 24, Week 72 and Week 96/WD only.
- Concomitant medication

- AEs
- Contact IXRS to obtain next kit numbers.
- Study drug administration (after all other visit assessments are completed and laboratory samples are drawn) (all visits except at Week 96/WD).
- Randomization at Week 48
- Check of sustained remission criteria (all visits except Weeks 2, 4, and Week 96/WD visit)

8.3.2 3 to 5 days prior to Week 48

- Blood samples will be collected for hematology and biochemistry analyses and CRP
- BASDAI
- BASFI
- SF-36
- ASQoL
- EQ-5D
- IBD-Q
- Total spinal pain NRS and nocturnal spinal pain NRS
- PtGADA
- Plasma for CZP concentration and ADAbs
- Plasma for biomarkers
- Genetics
- Blood sample will be collected for serum calprotectin
- AEs

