12.7.3 Assessment and management of TB and TB risk factors

As TNF antagonists are known to be associated with significant risk of reactivation of LTB, appropriate rigorous precautions are being taken within the protocol (see [Section 6.2](#) [Exclusion Criterion 16]) and [Section 6.3.1](#) [Withdrawal Criterion 7]).

Signs and Symptoms

The Investigator should consider all potential sites of infection when assessing for TB during the physical examination, and other evaluations, and based on the subject's history. Sites commonly infected by TB include: the lungs, larynx, lymph glands, pleura, gastrointestinal system, genito-urinary tract (including renal), bones and joints, meninges, peritoneum, pericardium, and skin. This is not an exhaustive list and unusual presentations and areas of involvement should always be considered.

Common symptoms with which the subject may present with include cough, blood in sputum, night sweats, lymphadenitis, joint pain/swelling, spinal deformity, headache/confusion, abdominal pain mimicking IBD, frequent or painful urination, scrotal mass in men and pelvic inflammatory disease in women as well as other symptoms, or nonspecific symptoms. This is not an exhaustive list and unusual presentations should always be considered.

Latent TB infection is defined as the absence of signs, symptoms (ie, evidence of organ-specific involvement), or physical findings suggestive of TB infection with a positive IGRA test (or 2 indeterminate IGRA test results) and a chest x-ray (or other imaging) without evidence of TB infection. If the result of the IGRA test is indeterminate, the particular IGRA test previously performed may be repeated once; if positive or indeterminate on retest, the subject may not be randomized to study medication without further evaluation, treatment, and discussion with the Study Physician, if LTB infection is identified. (If active TB is identified, subject must undergo appropriate study specified withdrawal procedures.) The retest must be done during the protocol-defined Screening window.

Note: If available, respiratory or other specimens must also be smear and culture negative for TB (CDC diagnosis of LTB infection, <http://www.cdc.gov/TB/topic/testing/default.htm>).

Test Conversion

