Tuberculosis test conversion is defined as a positive result (IGRA) for the current test but previous test results were negative (IGRA). All subjects with TB test conversion must immediately stop study drug administration. In case of a TB test conversion, the subject must be considered as having either a suspected new latent or an active TB infection and be promptly referred to an appropriate specialist (ie, pulmonologist, infectious disease specialist) for further evaluation. If test conversion indicates LTB infection, active TB, or nonmycobacterial TB infection then, per UCB TB working instructions, TB test conversion (confirmed) should be classified as due to LTB, active TB infection, or non-TB mycobacterial infection. Additional assessments (eg, blood tests or IGRA test, chest x-rays, or other imaging) should be performed as medically indicated.

Latent TB

In case the evaluation by the appropriate specialist indicates a new LTB, a prophylactic TB treatment (as described in **Section 6.2**, Exclusion Criterion 16) should be initiated and study medication can be continued no sooner than 4 weeks after start of prophylactic TB treatment, if it is deemed likely that prophylactic TB treatment is continued to completion.

In case no prophylactic treatment is initiated, the subject has to be withdrawn.

Every action should be discussed in advance with the Medical Monitor. Latent TB is an Adverse Event of special interest (AESI) and must be reported as such.

Active TB/nontuberculosis mycobacterium

Subjects who develop active TB or nontuberculosis mycobacterium (NTMB) infection during the study (conversion demonstrated by IGRA) must be withdrawn from the study. The subject must be immediately discontinued from study medication and a WD Visit must be scheduled as soon as possible, but no later than the next scheduled visit. The subject should be encouraged to keep the SFU Visit as specified by the protocol. The TB must be documented as an SAE. Treatment should be immediately started.

Note that subjects with history of or active NTMB infection are excluded from the study regardless of prior or current therapy.

Confirmed active TB is an SAE and an AESI and must be captured on an SAE report form and provided to the Sponsor in accordance with SAE reporting requirements. As with all SAEs, periodic follow-up reports should be completed as per protocol requirement until such time as the TB infection resolves.

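### Several latent-TB entry conditions are tied to randomization, a word the protocol uses for both Week 0 and Week 48, and their fit with the 5-week screening limit is not stated

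*Protocol*

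**What the plan says.** **Conditions tied to randomization.** Protocol Section 8.1 covers subjects who begin LTB treatment during screening. They must repeat the screening laboratory work, examinations and questionnaires "after receiving at least 4 weeks of treatment for LTB infection) prior to randomization in the study". The investigator must also judge completion of therapy to be likely, and record that opinion before the subject is randomized. Section 12.7.3 says that after a positive or indeterminate IGRA retest "the subject may not be randomized to study medication without further evaluation, treatment, and discussion with the Study Physician".

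**When randomization happens.** Section 7.10 sets it at Week 48, and the visit list in Section 8.3.1 agrees ("Randomization at Week 48"). The Week 0 list in Section 8.2, however, tells the site: "Contact IXRS to randomize subject and to obtain kit number". Open-label certolizumab pegol starts at Week 0 (Section 5.1.1).

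**Conditions tied to treatment.** Exclusion 16c (Section 6.2) bars latent TB "unless appropriate prophylaxis is initiated prior to study treatment and continued to completion of prophylaxis". Section 12.7.3.2 requires a chest x-ray clear of TB before the first dose. For LTB found during the study, Section 12.7.3 says "study medication can be continued no sooner than 4 weeks after start of prophylactic TB treatment", and Section 12.7.3.4 repeats that link to study medication.

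**Screening limit.** Section 8.1: "The period between the Screening and Baseline Visits must not exceed 5 weeks".

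**The concern.** The conditions in Section 8.1 read as safeguards to be met before exposure to a TNF antagonist. In a trial randomized at the first dose, the anchor would do no harm. Here exposure begins 48 weeks before randomization, and the protocol uses the same word for both dates.

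A site that takes Sections 7.10 and 8.3.1 as the definition can start dosing once prophylaxis has been initiated, and leave the 4-week interval, the repeat screening and the recorded opinion until Week 48. A site that takes Section 8.2 as the definition must fit all of them into screening. About 95 sites are planned (Section 5.1.5), so the same kind of subject could be handled in two ways. Both the safety conditions and eligibility for Part A would then depend on how the site reads one word.

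**Working it through.** **Inputs.** Randomization at Week 48 (7.10, 8.3.1); the word randomize at Week 0 (8.2); dosing every 2 weeks from Week 0 to Week 46 (Summary, 5.1.1); at least 4 weeks of LTB treatment and at most 5 weeks of screening (8.1).

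**The plan's own figure.** Section 5.1.4 gives a maximum of 109 weeks per subject. It reproduces: 5 + 48 + 48 + (10 − 2) = 109. The total contains 5 weeks of screening and no more. The only prolongation that section mentions is for subjects who flare in Part B.

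**Reading 1: randomization means Week 48.**

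- Dosing time points before randomization: 46/2 + 1 = 24. The first three are the 400mg loading doses.
- Still required before the first dose: prophylaxis initiated (16c), eligibility review at Baseline (8.2), clear chest x-ray (12.7.3.2).
- Not required before the first dose on the literal text: the 4-week interval, the repeat screening, the recorded opinion, and the Section 12.7.3 bar after an IGRA retest.
- Comparison: for LTB found during the study, the 4 weeks run to study medication. On this reading, LTB known at entry has a looser pre-dose timing rule than LTB found later.

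**Reading 2: randomization means Baseline.**

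- Days left in screening: 35 − 28 = 7.
- Let T be the days from the Screening Visit to the start of LTB treatment, and R the days needed after the 4 weeks to repeat the assessments and obtain results. The sequence fits if 28 + T + R ≤ 35, that is, T + R ≤ 7.
- The protocol gives neither T nor R. The values below are assumptions.

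| T (days) | R (days) | 28 + T + R | Within 35? |
|---|---|---|---|
| 2 | 5 | 35 | yes |
| 5 | 2 | 35 | yes |
| 7 | 0 | 35 | yes |
| 3 | 5 | 36 | no |
| 5 | 3 | 36 | no |
| 7 | 1 | 36 | no |
| 10 | 0 | 38 | no |

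T must also absorb any IGRA retest, which Section 12.7.3 places inside the screening window. Section 8.1 states no extension of the 5 weeks for these subjects.

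**The case against.** The strongest reply is that context points to entry into Part A. The sentence sits under the Screening Visit, concerns treatment begun in screening, and asks for screening tests to be repeated. Section 12.7.3 speaks of being randomized to study medication and keeps the retest within screening, and the next section, 8.2, uses the word for Week 0. Repeating screening tests at Week 48, after 24 dosing time points, would make little sense. This makes a Week 0 intention plausible, but the site has to infer it against Sections 7.10 and 8.3.1. It also leads straight to the tight screening window.

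Four stronger readings might tempt a reader, and the documents do not support them:

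- *No latent-TB safeguard applies for 48 weeks.* Exclusion 16c, the Baseline eligibility review and the chest x-ray rule all operate before dosing, and Section 12.7.3.4 requires subjects on LTB treatment at Baseline to complete the course.
- *A subject with latent TB cannot be enrolled at all.* Seven days remain, Section 8.1 recommends doing the IGRA first, and the chest x-ray may predate screening. Failure depends on turnaround times that are not given. Nor does Exclusion 1 ("Subject has previously participated in this study") settle whether re-screening is allowed; treating it as a bar is an inference.
- *The repeat tests conflict with the rule against IGRA testing in LTB subjects (12.7.3.4).* The IGRA is not in the laboratory list of Table 12.2 and has its own row in Table 5.1, so the instruction to repeat laboratory parameters need not include it.
- *A large number of subjects is affected.* The protocol gives no LTB prevalence, so no count can be derived.

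**Conclusion.** The point holds as a contradiction in an operational safety rule. Four conditions are exposed: the 4 weeks of LTB treatment, the repeat screening, the recorded opinion, and the bar after an IGRA retest. The protocol attaches them to a word that it places at Week 48 in two sections and at Week 0 in another.

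The two consequences are alternatives and do not add up. Under the Week 48 reading, 24 dosing time points can precede these conditions, although 16c and the chest x-ray rule still apply. Under the Baseline reading, at most 7 of 35 days remain for work-up and repeat tests; this is feasible only if they take 7 days or less in total. The 24 and the 7 follow from the protocol's own schedule. Whether 7 days is enough rests on durations the protocol does not state.

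**What to change.** The sponsor should reconcile Sections 6.2 (exclusion 16c), 7.10, 8.1, 8.2, 12.7.3 and 12.7.3.4 by amendment:

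1. Make each TB entry condition name one unambiguous event.
2. Use the word randomize only for Week 48, and remove it from the Week 0 list in Section 8.2.
3. State how the 4-week requirement relates to the 5-week screening limit, including whether any extension applies.
4. Check the zoledronic acid entry in Table 6.1, whose three-year look-back is also counted from randomization.

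Which event is right, and the clinical content of the TB rules, are for the sponsor and its TB experts; none is proposed here. The cost is amendment wording, plus a change to the IXRS screening window if the sponsor decides to allow an extension. The wording changes themselves add no study procedures.
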